APPENDIX B. ADJUDICATION CRITERIA FOR HEMOSTATIC EFFICACY

Excellent (effective)	• Change from baseline in NIHSS of +6 or less at the 12-hour time-point, AND the following imaging criteria:
	• $\leq 20\%$ increase in hematoma volume compared to baseline on a repeat CT or MRI scan performed at the 12-hour time-point.
	• No rescue therapies ^a administered between 3 hours and 12 hours after randomization.
Good (effective)	• Change from baseline in NIHSS of +6 or less at the 12-hour time-point, AND the following imaging criteria:
	• > 20% but ≤ 35% increase in hematoma volume compared to baseline on a repeat CT or MRI scan at any time between the completion of initial randomized treatment and the 12-hour time-point.
	• No rescue therapies ^a administered between 3 hours and 12 hours after randomization.
Poor/None (not effective)	• If a patient meets any one of the following criteria, they are considered to have poor/none hemostatic efficacy:
	• Change from baseline in NIHSS of +7 or more at the 12-hour time-point.
	• >35% increase in hematoma volume compared to baseline on a repeat CT or MRI scan performed at any time between the completion of initial randomized treatment and the 12-hour time-point.
	• Any initiation of rescue therapies greater than 3 hours after randomization and up to 12 hours post-randomization should result in poor/none hemostatic efficacy.
	• Any administration of and examet starting greater than 3 hours after randomization and up to 12 hours post-randomization should result in poor/none hemostatic efficacy.
	• Any surgical procedures specifically intended to treat the hematoma occurring between 3 hours after randomization and up to 12 hours post-randomization should result in poor/none hemostatic efficacy.
Not Evaluable	• Insufficient information available to determine change from baseline in NIHSS, OR
	• Insufficient imaging information (i.e., missing or uninterpretable imaging scan) to determine change from baseline in volume, OR
	• Insufficient information available to determine whether patient received rescue therapy.
	• These cases will be further adjudicated to determine if they are non-evaluable from administrative reasons (e.g., scan not available for technical reason, transfer to another facility, or hematoma drainage not due to clinical deterioration) or clinical reasons (scan not available because of patient deterioration). Cases assessed as non-evaluable for clinical reasons will be imputed as having poor/none hemostatic efficacy.

Note: This Appendix is intended only as a guide to Investigators and is not intended to be comprehensive. Full details on the rating of hemostatic efficacy are provided in the Adjudication Charter.

^a Rescue therapies defined as any pro-coagulant replacement factor products (e.g., 3- and 4-factor prothrombin complex concentrates, activated PCCs, FEIBA[®], recombinant fVIIa, plasma, FFP, whole blood), any systemic or local hemostatic therapies (except tranexamic acid), or the conduct of unplanned surgeries/procedures to treat the hematoma.

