	For a patient to have excellent or good hemostatic efficacy, he or she must meet all of the following criteria:			
	 NIHSS score of less than +7 point change from the baseline score at 12 hours post-randomization 			
	• No greater than 35% increase from baseline in hematoma volume at 12 hours post-randomization			
	• Have not received rescue therapy (as defined in Section 7.4) between 3 and 12 hours post-randomization			
	The following hypothesis will be evaluated:			
	H ₀ : $\pi_{\rm UC} - \pi_{\rm andexanet} = 0$			
	H_{A} : $\pi_{UC} - \pi_{andexanet} \neq 0$			
	Analysis will be performed using a Cochran-Mantel Haenszel (CMH) test stratified by time from symptom onset to baseline imaging scan (< 180 minutes vs \geq 180 minutes). The corresponding 95% confidence intervals for the difference in the proportion of participants with effective hemostasis between andexanet and usual care, and for the_proportions will be provided. Missing values and/or non-evaluable hemostatic efficacy will be imputed.			
	The study will be considered to have met its primary efficacy objective if (1) the proportion of and exanet-treated patients with effective hemostasis is significantly higher than that in patients randomized to usual care with p < 0.0310 at interim analysis when_approximately 50% (450 patients) of the anticipated sample size has been adjudicated for their hemostatic data; or (2) p < 0.0277 at the end of the study.			
	If the primary endpoint is statistically significant, the secondary endpoint will be tested at the same alpha level.			
	The secondary endpoint is the percent change in anti-fXa activity from baseline to nadir during the first 2 hours post-randomization. The analysis of this endpoint will be an Analysis of Covariance (ANCOVA) on the ranked data, including time from symptom onset to baseline imaging scan (< 180 minutes vs. \geq 180 minutes), and baseline anti-fXa activity as covariates.			
	The final analysis is controlled in a similar fashion using an alpha level of 0.0277.			
	The overall family-wise error rate is controlled at alpha level of 0.05 and accounts for the interim and final analyses for the primary and secondary endpoints.			
	Neurological status at 24 hours compared with baseline according to scoring on the NIHSS and GCS is included among the additional efficacy endpoints. The change from baseline to hour 24 for each scale will be analyzed using a linear mixed effects model while the binary			

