Note: Dosing procedures begin after randomization. Andexanet will be given as a bolus over 15-30 minutes followed by 120-minute continuous infusion. Treatment duration of usual care is dependent upon available therapy. A detailed listing of study procedures, including additional laboratory samples Day 1 through Day 30 is detailed in Appendix A.

Following baseline assessments, imaging evaluation will be performed at approximately 12 hours following randomization. All scans for individual patients should utilize a consistent imaging modality, scanner, and acquisition protocols/techniques whenever possible. Primary neurologic assessment will consist of evaluation of the National Institutes of Health Stroke Scale (NIHSS) at baseline and at 12 hours. The 12-hour and 24-hour assessments will be performed by study personnel who are blinded to the treatment allocation of the patient. Additional NIHSS measurements performed at 2 hours, 3 hours, 6 hours, and 72 hours will be performed for safety monitoring purposes; these measurements may be blinded or unblinded. Following the 12-hour assessment, patients will return for a follow-up visit at Day 30 (+7) and follow-up phone calls on Day 7 (+3) and Day 14 (+6). s (a detailed Schedule of Activities is provided in Appendix A). An additional visit is required for patients with a positive anti-andexanet antibody response at the Day 30 visit approximately 120 days post-randomization, or within 30 days of when the positive test is made known to the Investigator, whichever is later.

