The Phase 2 and Phase 3 trials of andexanet used reversal of anticoagulation endpoints as assessed by anti-fXa activity, anticoagulant free fraction, and thrombin generation. In this study, hemostatic efficacy is being studied as the primary efficacy outcome, while the reversal of anticoagulation is being investigated as the secondary efficacy outcome. The timing of all endpoints is anchored on randomization.

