3.3.2.1. Hemostatic Efficacy

Because of the clinical importance of hematoma expansion, CT/MRI-based volumetric measurement is considered to be the most direct way to evaluate hemostatic efficacy and will

constitute the primary assessment of this endpoint. That said, it is acknowledged that an evaluation of clinical status is potentially important to better ascertain the global benefit of an intervention. In the acute phase, the best clinical measure of focal neurologic change is captured by the NIHSS (Appendix E). Accordingly, for the purposes of evaluating the primary endpoint, the NIHSS will be measured by blinded personnel at 12 hours following randomization.

In addition, another important clinical metric of efficacy is the durability of therapy. Therefore, the use of pro-coagulant factor infusions (e.g., 3- or 4-factor PCC/activated PCC, rfVIIa, plasma, fresh frozen plasma [FFP] and anti-inhibitor coagulant complex [e.g., FEIBA[®]]), whole blood (see Table 5), hemostatic therapies, or an intervention/surgery intended to treat the hematoma at any time between 3 and 12 hours after randomization will result in the patient being considered having poor/none hemostatic efficacy in both treatment groups.

Given the above considerations, the adjudication of hemostatic efficacy will be based on a combination of imaging and clinical findings (Appendix B). If a patient has an increase in hematoma volume > 35% from baseline at any time between the end of initial randomized treatment and 12 hours post-randomization, they will be considered to have poor/none hemostatic efficacy. Additionally, if a worsening from baseline in NIHSS score of +7 or more is observed at 12 hours, a patient will be considered to have poor/none hemostatic efficacy. Finally, if a patient receives rescue therapy (as delineated above), they will also be considered to have poor/none hemostatic efficacy. Overall, if a patient should meet any one of the above criteria, they will be considered to have "symptomatic hematoma expansion" (see Section 7.4).

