10.5.3.1. Primary Efficacy Endpoint

The primary efficacy endpoint is based on the achievement of effective hemostasis 12 hours post-randomization, as determined by the blinded EAC, based on pre-specified criteria documented in the Adjudication Charter (see Appendix B).

Effective hemostasis will be further defined as:

- 1 = for patients with hemostatic efficacy rated by the EAC as excellent or good, and
- 0 = for patients with hemostatic efficacy rated by the EAC as poor/none.

For a patient to have excellent or good hemostatic efficacy, he or she must meet all of the following criteria:

- NIHSS score of less than +7 point change from the baseline score at 12 hours post-randomization.
- No greater than 35% increase from baseline in hematoma volume within 12 hours post-randomization.
- Has not received rescue therapy (as defined in Section 7.2, Section 7.3, and Section 7.4) between 3 and 12 hours post-randomization

If data supporting either the imaging or clinical components of the adjudication of hemostatic efficacy are missing, out-of-window, uninterpretable or confounded (e.g., intubation or sedation), cases will be referred for external adjudication by EAC. Procoagulant blood products administered within 3 hours post-randomization to patients randomized to andexanet will be reviewed by EAC to determine if they were related to clinical or administrative reasons. Surgeries or procedures impacting hematoma volume within 3 hours post-randomization will also be reviewed by EAC to determine if related to clinical or administrative reasons (see Section 7.2, Section 7.3, and Section 7.4).

Cases where it is determined that there is insufficient information, or when it is not otherwise possible to properly assess the effect of treatment, will be further classified by the EAC as 'non-evaluable due to administrative reasons' (e.g., follow-up scan not available/ performed/ interpretable, patient transferred to another facility for administrative purposes) or 'non-evaluable due to clinical reasons' (e.g., patient died, patient had unplanned surgery draining hematoma).

All ITT patients will be included in the primary analysis. Patients with non-evaluable hemostatic efficacy due to clinical reasons will be treated as treatment failures (similar to patients with poor/none hemostatic efficacy). Both non-evaluable subjects due to administrative and clinical reasons will be included in the denominator for primary efficacy analysis.

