 - Confounded assessments (eg crossover or due to sedation or intubation)
 - Imaging (CT or MRI):
 - Imaging is missing at baseline and/or 12 hours post-randomization
 - Baseline imaging is >2 hours prior to randomization or postrandomization
 - 12-hour imaging is <11 hours or >15 hours post-randomization
 - Confounded assessments (eg inconsistent imaging modality)

Effective Hemostasis

Effective hemostasis is assessed based on image evaluation (CT or MRI), NIHSS score, and use of rescue therapy and categorized into excellent, good, or poor/none. Imaging will be performed at baseline and 12 hours post-randomization and should utilize a consistent imaging modality for both time points to minimize technical discrepancy (ie, CT or MRI scan). NIHSS evaluation

Page 36 of 52 Alexion Confidential (blinded or unblinded) to inform effective hemostasis will be performed at baseline (prior to randomization) and at 2, 3, 6, and 72 hours post-randomization. Blinded NIHSS evaluation will occur at 12 and 24 hours post-randomization. Use of rescue therapy (including procedures intended to treat the hematoma) between > 3 and < 12 hours post-randomization will be considered a treatment failure (ie, poor/none effective hemostasis).

Effective hemostasis will be further defined as follows:

- 1 = for participants with effective hemostasis rated as excellent/good
- 0 = for participants with effective hemostasis rated as poor/none

For a participant to have excellent or good effective hemostasis, he or she must meet all of the following criteria:

- An NIHSS score of less than +7-point change from the baseline score at 12 hours post-randomization
- An increase of no greater than 35% from baseline in hematoma volume between baseline and 12 hours post-randomization
- No rescue therapy received between 3- and 12-hours post-randomization

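### Two protocol texts open the hematoma-expansion window when randomized treatment ends, a point that differs by arm and does not exist for untreated usual care; the window should be stated once, from randomization

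*Protocol*

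**What the plan says.** The documents describe the imaging window in several ways.

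- **Protocol Appendix B, Poor/None row:** growth above 35% counts on a repeat scan "performed at any time between the completion of initial randomized treatment and the 12-hour time-point". The Good row carries the same anchor. The Excellent row refers only to the 12-hour scan.
- **Protocol 3.3.2.1:** growth above 35% counts "at any time between the end of initial randomized treatment and 12 hours post-randomization".
- **Protocol 3.3.2:** "The timing of all endpoints is anchored on randomization".
- **Protocol 10.5.3.1 (primary endpoint):** "No greater than 35% increase from baseline in hematoma volume within 12 hours post-randomization". This section also refers the reader to Appendix B and the Adjudication Charter.
- **Protocol synopsis, statistical analysis:** "No greater than 35% increase from baseline in hematoma volume at 12 hours post-randomization".
- **SAP 6.1:** "An increase of no greater than 35% from baseline in hematoma volume between baseline and 12 hours post-randomization". SAP 5.5.5 defines the imaging parameter as the change in volume between baseline and 12 hours, and the classification algorithm in SAP 6.1 works with a 12-hour scan taken at 11 to 15 hours.

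On when treatment ends, the note to Figure 1 in Protocol 3.1 says "Treatment duration of usual care is dependent upon available therapy". Usual care may be no treatment, and Appendix A (footnote 8) lets it begin at any time up to 3 hours after randomization.

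**The concern.** A failure criterion for the primary endpoint should observe both arms over the same period. A window that opens when treatment finishes does not do so, because andexanet has a roughly fixed two-hour infusion and usual care has no fixed length. For usual care without treatment the rule cannot be applied. SAP 6.1 gives such patients a start of treatment (the randomization date) but no completion.

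The texts also disagree on whether a scan before the 12-hour scan can count at all. SAP 6.1 expects most cases to be classified by algorithm without adjudicator review, so one window has to be programmed and the documents do not settle which. Early scans are possible: Protocol 7.3 lets unblinded investigators scan at any time for medical reasons, and Protocol 3.4 asks for a scan after an NIHSS rise of 5 or more. The first scheduled NIHSS is at 2 hours, before an on-schedule andexanet infusion has ended.

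**Working it through.** **1. When andexanet treatment ends.** Inputs from Protocol 6.2: start 0 to 30 min after randomization, bolus about 15 min (low) or 30 min (high), infusion 120 min.

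End = start + bolus + infusion.

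- Low dose: 0 + 15 + 120 = 135 min to 30 + 15 + 120 = 165 min.
- High dose: 0 + 30 + 120 = 150 min to 30 + 30 + 120 = 180 min.
- From the target rates: 400/30 + 480/4 = 133 min and 800/30 + 960/8 = 147 min; with a start at 30 min, 163 and 177 min.

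**2. When usual care ends.** The documents give no duration. Assume a product given in 10 to 30 min.

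- Started at once: ends at 10 to 30 min.
- Started at 2 h 45 min (165 min, allowed): ends at 165 + 10 = 175 to 165 + 30 = 195 min.
- No treatment: undefined.

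**3. One patient under each text.** Growth is +50% on an unscheduled scan at 90 min and +15% at 12 hours, with no NIHSS or rescue failure.

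| Text | Andexanet | Usual care, early short infusion | Usual care, started at 165 min | Usual care, no treatment |
|---|---|---|---|---|
| 3.3.2.1, Appendix B | not a failure | failure | not a failure | undefined |
| 10.5.3.1 | failure if any scan counts (not stated) | same | same | same |
| Synopsis | not a failure | not a failure | not a failure | not a failure |
| SAP 5.5.5, 6.1 | not a failure | not a failure | not a failure | not a failure |

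Only the first row depends on the arm.

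**4. The asymmetry can reverse.** Put the early scan at 170 min. For low-dose andexanet started at once, treatment ended at 135 min and the scan counts. For usual care started at 165 min, treatment ends at 175 min or later and the scan does not count.

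**5. Scale, on assumed shares.** The design figures reproduce. Pocock-type spending at half the information is 0.05 × ln(1 + (e − 1) × 0.5) = 0.0310, and the final nominal level is 0.0277. Two-look power with 450 per arm, 70% versus 80%, is 91.2% without dropout and 89.7% with 5% dropout, against the stated 90% or so.

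Let x be the share of an arm whose only failure is growth above 35% on a scan before treatment completion. The documents give no value. In the extreme case where every such usual-care patient counts and no andexanet patient does, the observed difference shifts by x. With a true rate of 70% in both arms, two-sided rejection over both looks is:

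| x (assumed) | Patients per 450 | Rejection |
|---|---|---|
| 0.25% | 1.1 | 5.06% |
| 0.5% | 2.3 | 5.25% |
| 1% | 4.5 | 6.0% |
| 2% | 9 | 9.2% |

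These are upper bounds for each x. By symmetry the totals are the same if the arms are swapped.

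**The case against.** The case against is strong on several counts, and most of it stands.

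- **Early growth is not exempt under andexanet.** A reader might infer that expansion in the first 2 to 3 hours cannot count in that arm, or that 19% to 25% of the 12-hour window (135/720 to 180/720) goes unobserved. The documents do not support this. Volume is compared with a pre-randomization baseline at a 12-hour scan scheduled for everyone, so growth that persists above 35% is Poor/None in both arms. A missing 12-hour scan that leaves the case non-evaluable is scored as poor/none under the SAP. NIHSS worsening at 12 hours, or rescue between 3 and 12 hours, also still counts.
- **Direction.** A reader might infer a bias in favour of andexanet. That needs usual care to finish first, and step 4 shows that it need not.
- **Timing of risk.** Protocol 3.3.1 places the greatest expansion risk within 3 hours of symptom onset, not of randomization. Randomization may fall up to 6 + 2 = 8 hours after onset, so that statement does not show that the early post-randomization period is the critical one.
- **Frequency.** No rate of early scans is given, and Protocol 7.3 describes the triggering deficit as one found after initial treatment.
- **Status of the text.** Appendix B calls itself a guide to the Adjudication Charter, which is not available, and the SAP derivation does not use the anchor.

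The last point does not remove the conflict. Protocol 3.3.2.1 repeats the anchor in the body of the protocol, and 10.5.3.1 itself points to Appendix B.

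**Conclusion.** The conflict is real and concerns a component of the primary endpoint. Protocol 3.3.2.1 and Appendix B use a starting point that varies by arm, is undefined for an allowed form of usual care, and contradicts the protocol's own statement that endpoints are timed from randomization. The consequence is narrow. Classification differs by arm only when an unscheduled scan before treatment completion shows growth above 35%, the 12-hour scan is at or below 35%, and nothing else makes the patient a failure. Few such patients are likely. Each 1% of an arm would move the treatment difference by at most 1 point of the planned 10, in a direction that the documents do not fix. The figures in step 5 rest on assumed shares and estimate nothing about this trial. Planned sample size, power and alpha are unaffected.

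**What to change.** Delete the treatment-completion anchor from Protocol 3.3.2.1 and from the Good and Poor/None rows of Appendix B. State one window, timed from randomization and identical in both arms, in the synopsis, 3.3.2.1, 10.5.3.1, Appendix B, SAP 5.5.5, SAP 6.1 and the Adjudication Charter.

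The simplest version is the comparison already in the SAP: baseline scan against 12-hour scan. It is symmetric and does not depend on who was scanned early. If the sponsor wants unscheduled scans to count, they should count from randomization in both arms. That choice changes the SAP definition, and because unblinded investigators order these scans, more scanning in one arm would create more chances to fail there.

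The cost is wording, and possibly a few patients reclassified. No new scans are needed, since the core laboratory already reads all available ones.

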APPENDIX C. GLASGOW COMA SCALE (GCS)

Score	Criterion
Eye Open	ing
4	Open before stimulus
3	After spoken or shouted request
2	After fingertip stimulus
1	No opening at any time, no interfering factor
NT	Closed by local factor
Verbal Re	esponse
5	Correctly gives name, place, and date
4	Not orientated but communication coherently
3	Intelligible single words
2	Only moans/groans
1	No audible response, nom interfering factor
NT	Factor interfering with communication
Best Moto	or Response
6	Obey 2-part request
5	Brings hand above clavicle to stimulus on head/neck
4	Bends arm at elbow rapidly but features not predominantly abnormal
3	Bends arm at elbow, features clearly predominantly abnormal
2	Extends arm at elbow
1	No movement in arms/legs, no interfering factor
NT	Paralyzed or other limiting factor

NT = Not testable

APPENDIX D. MODIFIED RANKIN SCALE (MRS)

Score	Description
0	No symptoms at all
1	No significant disability despite symptoms; able to carry out all usual duties and activities
2	Slight disability; unable to carry out all previous activities, but able to look after own affairs without assistance
3	Moderate disability; requiring some help, but able to walk without assistance
4	Moderately severe disability; unable to walk without assistance and unable to attend to own bodily needs without assistance
5	Severe disability; bedridden, incontinent, and requiring constant nursing care and attention
6	Dead

